3.3 HYPOTHESIS

The overarching hypothesis is that administration of corticosteroids to pregnant women with either pre-gestational or gestational diabetes within 7 days prior to planned CS where CS is scheduled between 35⁺⁰ weeks and 39⁺⁶ gestation will reduce the incidence and severity of neonatal respiratory morbidity without adverse short-term (within the first 6 weeks) consequences for the mother or baby.

Specifically, we hypothesise that administration of corticosteroids to women with pre-gestational or gestational diabetes within 7 days prior to planned CS, where CS is scheduled between 35⁺⁰ weeks and 39⁺⁶ gestation, will:

1. reduce the incidence and severity of neonatal respiratory morbidity.
2. not increase the incidence of neonatal hypoglycaemia.
3. not increase the incidence of maternal morbidity (hyperglycaemia, chorioamnionitis, endometritis, or wound infection).
4. increase breast feeding rates at hospital discharge and 6 weeks post-partum.
5. reduce health care costs.

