7.1 Participant Risk Management and Safety	26
7.2 Handling of Withdrawals.....	27
7.3 Replacements.....	28
7.4 Trial Risks	28
8. Statistical Methods	28
8.1 Sample Size Estimation & Justification.....	28
8.2 Statistical Methods To Be Undertaken.....	29
8.3 Interim analyses.....	29
9. Supply and Accountability of Investigational Product	30
9.1 Drug Accountability	30
10. Storage of Blood and Tissue Samples	30
11. Data Security & Handling	30

11.1	Details of where records will be kept & How long they will be stored	30
11.2	Confidentiality and Security	31
11.3	Access to Data and Data Sharing	31
12.	SAFETY REPORTING.....	31
13.	Trial Committees.....	33
14.	Publication Policy	34
15.	Funding.....	35
16.	Appendix	36
17.	References	42

STUDY SYNOPSIS

Title:	PRECeDe Trial: P revention of neonatal R espiratory distress with antenatal corticosteroids prior to E lective C aesarean section in women with D iabetes - A Randomised Trial
Short Title:	PRECeDe RCT
Design:	Triple blind, placebo controlled, randomised controlled trial (RCT) to assess whether antenatal corticosteroids reduce the incidence of neonatal respiratory distress when given to women with diabetes prior to an elective caesarean section (CS) planned between 35 ⁺⁰ and 39 ⁺⁶ weeks' gestation.
Study Question:	Does administration of antenatal corticosteroids to women with pre-gestational or gestational diabetes where birth by elective CS is planned between 35 ⁺⁰ weeks and 39 ⁺⁶ weeks of gestation, reduce neonatal respiratory morbidity without adverse consequences for mother or baby?
Primary Objective:	To determine whether administering antenatal corticosteroids to women with either pre-gestational or gestational diabetes who plan to give birth by elective CS between 35 ⁺⁰ weeks and 39 ⁺⁶ weeks' gestation reduces the rate of neonatal respiratory morbidity requiring admission to the neonatal nursery and any form of respiratory support (e.g. intermittent positive pressure via an endotracheal tube, nasal continuous positive airway pressure (CPAP), Hi- or Lo-flow oxygen/air mixture, or increased ambient oxygen delivered into an incubator) for ≥60 minutes at any time following birth.

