Secondary Objectives:	
 1. To determine whether administering antenatal corticosteroids to women with either pre-gestational or gestational diabetes who plan to give birth by elective CS between 35⁺⁰ weeks and 39⁺⁶ weeks' gestation: 
 • increases the rate of short-term non-respiratory morbidity (eg neonatal hypoglycaemia, neonatal nursery admission and length of stay) in the infant; • increases the rate of maternal morbidities (eg maternal hyperglycaemia, infection); • has a favourable cost-effectiveness ratio 2. To assess the extent to which participants, clinicians and researchers remain blinded to the treatment allocation (in a subset of participants). 3. To establish a cohort of children to evaluate the longer term outcomes at 2 years, 6-7 years and 10-12 years following corticosteroid exposure in infants

	of mothers with diabetes (including cardiovascular, respiratory, metabolic, and neurocognitive function).
Inclusion Criteria:	
Women with a singleton or twin pregnancy who have a planned elective CS scheduled between 35⁺⁰ and 39⁺⁶ weeks' gestation who have pre-gestational diabetes OR gestational diabetes (diagnosed on a pregnancy 75 g oral glucose tolerance test according to the national Australian or New Zealand criteria for gestational diabetes (GDM) or via the modified criteria for diagnosis of GDM during the COVID-19 pandemic recommended by the Royal Australian New Zealand College of Obstetricians and Gynaecologists and Australasian Diabetes in Pregnancy Society)
 
AND
 
plan to give birth by elective CS within the next 7 days, between 35⁺⁰ and 39⁺⁶ weeks gestation (randomisation can occur within the week prior to 35⁺⁰ weeks as long as the CS is scheduled on or after 35⁺⁰ weeks gestation)

Exclusion Criteria:	
 1. Known major fetal anomaly or chromosomal anomaly. 2. Administration of intramuscular antenatal corticosteroid therapy for fetal lung maturation at any time during the pregnancy prior to randomisation. 3. Maternal systemic fungal infection 4. Maternal thrombocytopaenia with platelet count below 80x10⁹ /litre 5. Hypersensitivity to betamethasone sodium phosphate, betamethasone acetate, or other corticosteroids 6. Other contraindication to corticosteroids 7. Previous participation in the PRECeDe trial (prior participation in the PRECeDe Pilot trial is NOT regarded as an exclusion from participation in the current trial)

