Number of Planned Subjects:	2200 mothers (and their infants)
Investigational product:	11.4 mg of Celestone Chrondose in 2ml (betamethasone 11.4 mg, as betamethasone sodium phosphate and betamethasone acetate)

	Two injections will be administered intramuscularly, 24 hours apart, to participants randomised to receive the investigational product.
Placebo	Normal saline in an identical appearing syringe.
Safety considerations:	
Betamethasone is used extensively as part of the antenatal care in women at risk of giving birth prematurely. There is abundant literature supporting the safety of this drug in pregnant women. Betamethasone is associated with maternal hyperglycaemia and has been reported in one study to increase the risk of neonatal hypoglycaemia.
 
Observational studies have reported an increase in the risk of mild adverse neurocognitive outcomes (eg learning problems) in children who were exposed to antenatal corticosteroids prior to 35⁺⁰ weeks but were subsequently born at term. There are no studies evaluating the long term neurocognitive outcomes of children exposed to corticosteroids after 35⁺⁰ weeks and who birthed within 7 days of corticosteroid exposure.
 
There are currently no other safety concerns with respect to this drug.

Statistical Methods:	
Outcomes will be compared between the intervention and control groups using an intention-to-treat analysis. For all binary outcomes the magnitude of the between-group differences will be quantified by fitting a logistic regression model to estimate the odds ratio (OR) and 95% confidence interval (CI) for the corresponding population OR, stratified by site, type of diabetes (Type 1 diabetes, Type 2 Diabetes, Gestational Diabetes), and gestation at planned elective CS (35⁺⁰ to 36⁺⁶ weeks, 37⁺⁰ to 38⁺⁶ and 39⁺⁰ to 39⁺⁶ weeks).
 
Linear regression will be used for non-categorical outcomes.
 
For infant outcomes, models will be fitted using Generalised Estimating Equations to allow for non-independence of outcomes among twins from the same pregnancy.

Trial Registration:	The trial is registered with ANZCTR TBC
Funding:	NHMRC Clinical Trials and Cohort Studies Grant 2014750 ([name])

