8. STATISTICAL METHODS

8.1 SAMPLE SIZE ESTIMATION & JUSTIFICATION

A sample size of 2200 mothers (1100 in each arm, with continuity correction and allowing for 3% drop-out) will have 90% power to detect a relative reduction of 50% (absolute reduction of 3%) in neonatal respiratory distress from 6% to 3% with two-sided alpha of 0.05. This sample size will provide over 80% statistical power to detect a clinically significant increase of 30% in the secondary outcome of neonatal hypoglycaemia requiring treatment other than feeding

from 16% (from our pilot data for gestational diabetes and pre-gestational diabetes) to 20.8%.^{50,65}

We have used the following to inform our sample size:

- The effect size for the primary outcome of 50% reduction in rate of respiratory distress is based on the ASTECS study (RR 0.46, 95% CI 0.23 – 0.93),³⁷ and is consistent with the effect size observed in the meta-analysis of antenatal corticosteroids for late preterm and term infants (RR 0.74 95% CI 0.61 – 0.91 overall and RR 0.40, 95% CI 0.27 – 0.59 when the analysis is restricted to those delivering by planned CS after 37 weeks).⁶⁶ We consider a 50% reduction in the rate of respiratory distress requiring intervention for ≥ 60 minutes to be clinically relevant and likely to result in significant cost savings by preventing admissions to the neonatal nursery.
- The baseline prevalence of respiratory morbidity in neonates born to mothers with pre-gestational and gestational diabetes is estimated at 6% based on our preliminary studies from Sunshine Hospital and The Royal Women's Hospital. We have allowed for the higher prevalence of respiratory morbidity in babies born to women with pre-gestational diabetes (9% - Table 1) than to women with gestational diabetes (3-10%), but the lower prevalence of pre-gestational diabetes than that of gestational diabetes. This prevalence of respiratory morbidity is consistent with that observed in the ASTECS trial³⁷ (baseline prevalence of respiratory distress of 5.1%) and in the meta-analysis of antenatal corticosteroids in late preterm and term infants (7.2% in controls).⁶⁶

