8.2 STATISTICAL METHODS TO BE UNDERTAKEN

We will undertake descriptive statistical analysis reporting the proportion of women screened, eligible, approached, consented and refused as well as the time taken to complete study procedures.

Outcomes will be compared between the intervention and control groups using an intention-to-treat analysis. For all binary outcomes the magnitude of the between-group differences will be quantified by fitting a logistic regression model to estimate the odds ratio (OR) and 95% confidence interval (CI) for the corresponding population OR, stratified by recruitment site, type of diabetes (Type 1 diabetes, Type 2 Diabetes, Gestational Diabetes), and gestation at planned elective CS (35⁺⁰ to 36⁺⁶ weeks, 37⁺⁰ to 38⁺⁶ and 39⁺⁰ to 39⁺⁶ weeks). Linear regression will be used for non-categorical outcomes. For infant outcomes models will be fitted using Generalised Estimating Equations to allow for non-independence of outcomes among twins from the same pregnancy.

Assessment of blinding will be undertaken using Kappa statistic to assess the correlation between the participant or staff members "guess" of the allocation and the true allocation.

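### The no-increase hypotheses for neonatal hypoglycaemia and maternal morbidity have no limit of harm to be excluded, and hypothesis 3 includes maternal hyperglycaemia, an effect the protocol itself attributes to the drug

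*Protocol*

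**What the plan says.** **Claims of no harm.** The study question in the synopsis asks whether treatment will "reduce neonatal respiratory morbidity without adverse consequences for mother or baby". Section 3.3 carries this into the overarching hypothesis ("without adverse short-term (within the first 6 weeks) consequences for the mother or baby") and two specific ones. Hypothesis 2 is that treatment will "not increase the incidence of neonatal hypoglycaemia". Hypothesis 3 is that it will "not increase the incidence of maternal morbidity (hyperglycaemia, chorioamnionitis, endometritis, or wound infection").

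**Objectives worded the other way.** The secondary objectives in the synopsis ask whether treatment "increases the rate of short-term non-respiratory morbidity" in the infant, and likewise for maternal morbidities. That is a search for harm rather than a claim of its absence.

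**Design support.** Section 8.1 states "over 80% statistical power to detect a clinically significant increase of 30% in the secondary outcome of neonatal hypoglycaemia requiring treatment" beyond feeding, from 16% to 20.8%. It gives no such figure for any maternal outcome, nor for the other hypoglycaemia outcome in section 4 (any glucose below 2.6 mmol/l).

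**Analysis.** Section 8.2 says "For all binary outcomes the magnitude of the between-group differences will be quantified by fitting a logistic regression model", reported as an odds ratio with a 95% confidence interval. It names no non-inferiority margin and no bound to be excluded.

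**Known effect.** The synopsis, under safety considerations, says "Betamethasone is associated with maternal hyperglycaemia". Section 3.2 says that antenatal corticosteroids contribute to transient maternal hyperglycaemia, and section 7.1 lists it among the potential side effects.

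**The concern.** A hypothesis of no increase needs a stated amount of increase that the data must rule out. Power to detect an increase answers a different question: how often a real excess of a given size would reach significance. If the excess does not reach significance, that calculation gives no basis for saying there is none. The protocol supplies a clinically significant increase for one outcome but does not connect it to the hypothesis.

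The safety half of the study question is at stake. Hypoglycaemia is a live concern in the protocol's own background: section 3.2 cites an odds ratio of 1.60 (95% CI 1.37 to 1.87) from a late preterm trial, and Table 1 gives 1.70 (0.98 to 2.97) for hypoglycaemia needing intravenous therapy. The risk of misreading is also realistic. Section 3.2 presents a hazard ratio of 1.17 (0.37 to 3.69) for severe intellectual disability as no significant increase, and section 7.1 presents the same figures as no association. That interval does not exclude a more than threefold rise.

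Hypothesis 3 has a separate problem. It predicts no increase in an effect the protocol already ascribes to the drug, so as worded it conflicts with the protocol's own text.

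**Working it through.** **Inputs.** From section 8.1: 1100 per arm, 3% drop-out, two-sided alpha 0.05, 6% versus 3% for the primary outcome, 16% versus 20.8% for treated hypoglycaemia. Evaluable per arm: 1100 × 0.97 = 1067. All calculations are unadjusted and count one infant per mother.

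**1. Reproduce the protocol's figures.**
- Primary: the two-proportion formula for 6% versus 3% at 90% power gives 1002 per arm, or 1068 with continuity correction. Then 1068/0.97 gives 1102 per arm, 2204 in total, against the stated 2200. It reproduces.
- Treated hypoglycaemia at 1067 per arm, mean rate 0.184: Φ[(0.048√1067 − 1.96√(2 × 0.184 × 0.816)) / √(0.16 × 0.84 + 0.208 × 0.792)] = Φ[(1.568 − 1.074)/0.547] = Φ(0.903) = 81.7%, or 80.2% with continuity correction. The claim of over 80% reproduces.

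Both are calculations for detecting a difference.

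**2. What a non-significant result leaves open.** Hold the control rate at 16% and find the largest excess d with d = 1.96 × SE(d).
- At d = 0.0323 the treated rate is 0.1923. SE = √[(0.16 × 0.84 + 0.1923 × 0.8077)/1067] = 0.01648, and 1.96 × SE = 0.0323.
- Upper 95% limit: 0.0323 + 0.0323 = 0.0646, or +6.5 points; 0.0646/0.16 = 40% relative.
- The protocol's clinically significant increase: 0.208 − 0.16 = 0.048, or +4.8 points (30% relative).
- On the planned odds-ratio scale the same result is (0.1923/0.8077)/(0.16/0.84) = 1.25, with SE of the log = √[1/(1067 × 0.1344) + 1/(1067 × 0.1553)] = 0.114. The upper limit is exp(0.223 + 1.96 × 0.114) = 1.56. The 30% increase is an odds ratio of (0.208/0.792)/(0.16/0.84) = 1.38.

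**3. How often a real excess would be missed.** Power at 1067 per arm is 82% for a true 30% relative increase and 49% for 20%. The chance of a non-significant result is therefore 18% and 51%.

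**4. Power to exclude the protocol's own 30% increase if there is truly no effect.** Both arms at 16%, upper limit of the two-sided 95% interval:

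| Scale | Limit | SE | Power |
|---|---|---|---|
| Risk difference | 0.048 | √(2 × 0.1344/1067) = 0.0159 | Φ(0.048/0.0159 − 1.96) = 86% |
| Odds ratio | ln 1.38 = 0.321 | √(2/(1067 × 0.1344)) = 0.118 | Φ(0.321/0.118 − 1.96) = 78% |
| Risk ratio | ln 1.30 = 0.262 | √(2 × 0.84/(0.16 × 1067)) = 0.0992 | Φ(0.262/0.0992 − 1.96) = 75% |

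A tighter limit is less well served: on the risk-difference scale, 4 points has 71% power and 3 points 47%.

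**5. The other outcomes.**
- Any hypoglycaemia: section 3.2 gives a background rate of 50%. Excluding an assumed 5-point excess has power Φ(0.05/√(0.5/1067) − 1.96) = 64%.
- Maternal events: the protocol gives no control rates. Assuming 3%, 5% or 10%, power to detect a 30% relative increase is about 21%, 32% or 58%.

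**The case against.** The strongest reply is that section 8.2 plans estimation, not testing. It specifies an odds ratio with a 95% confidence interval and names no test or significance rule, so the upper limit a reader needs will be reported. This stands. A reader might infer that the safety outcomes are analysed only as tests of difference, or that the protocol will treat non-significance as proof of no harm. The documents support neither: no such decision rule appears, and the secondary objectives are worded as a search for harm. What is missing is the value against which the interval is to be read.

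A second reply is that an interpretation rule may sit in the statistical analysis plan, which is not shown. That is fair for the details of analysis. But the hypotheses, the clinically significant increase and the power statement are all fixed in the protocol, and the mismatch between them is visible there.

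A third reply is that the increase a trial is powered to detect is not automatically the harm it may tolerate. The protocol calls 30% clinically significant and nowhere calls a smaller excess acceptable. This stands too. The 30% figure is the loosest limit consistent with the protocol's own words, and a tighter one is for the trial team to justify. Nor does the present size comfortably support such a rule on every scale: the 86% applies only to the risk difference, and the ratio scales fall below 80%.

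**Conclusion.** The point holds at moderate severity. Section 3.3 states no-increase hypotheses. For neonatal hypoglycaemia, section 8.1 supports this only with power to detect a 30% rise in the treated form. For maternal morbidity it gives no important difference and no power. A non-significant result for treated hypoglycaemia could be read as no increase while its interval reaches +6.5 points, beyond the protocol's own +4.8. A true 30% excess would be non-significant 18% of the time. These figures assume a 16% control rate, 1067 evaluable per arm and unadjusted comparisons.

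Hypothesis 3 is also inconsistent with the synopsis and section 3.2 on maternal hyperglycaemia, and this does not depend on any calculation.

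The primary outcome, its analysis and the sample size are unaffected.

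**What to change.** 1. In sections 3.3 and 8.2, state that no increase in treated hypoglycaemia (treatment beyond milk feeding) will be concluded only if the upper limit of the planned two-sided 95% confidence interval excludes the protocol's own 30% increase: 16% to 20.8%, an odds ratio of about 1.38. Otherwise report that a clinically significant increase was not excluded. The trial team may justify a tighter limit.
2. Name the scale for this rule and state its power if there is truly no effect: about 75% for a risk ratio of 1.30, 78% for an odds ratio of 1.38, 86% for a risk difference of 4.8 points. The odds ratio keeps to section 8.2; a risk difference would add an effect measure.
3. Report any glucose below 2.6 mmol/l and the maternal infection outcomes as estimates with confidence intervals, without a no-increase claim.
4. Reconcile hypothesis 3 with the synopsis and section 3.2: take maternal hyperglycaemia off the no-increase list and report it as an estimate with a confidence interval.

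The cost is wording in the protocol and the statistical analysis plan, with no added participants if the 30% limit is kept and the stated power is accepted. The downside is that the no-increase claim becomes harder to make.

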3.4 STUDY AIMS

Primary Aim: To measure the effect of maternal betamethasone administration (compared with normal saline placebo) on the incidence of neonatal respiratory morbidity requiring admission to the neonatal nursery and any form of respiratory support (e.g. intermittent positive pressure via an endotracheal tube, nasal continuous positive airway pressure (CPAP), Hi- or Lo-flow oxygen/air mixture, or increased ambient oxygen delivered into an incubator) for ≥ 60 minutes at any time following birth.

Secondary Aims:

1. To measure the effect of maternal betamethasone administration (compared with normal saline placebo) on a range of health outcomes for the mother and infant(s) (specific outcomes described in Section 4.3)
2. To undertake a cost effectiveness analysis of the intervention
3. To establish and maintain a cohort of sufficient size to undertake future longer term studies to evaluate childhood health and neurocognitive outcomes (these studies will be the subject of future applications)

4. OUTCOME MEASURES

Primary outcome: Respiratory morbidity, defined as requiring admission to the neonatal nursery and any form of respiratory support (e.g. intermittent positive pressure via an endotracheal tube, nasal continuous positive airway pressure (CPAP), Hi- or Lo-flow oxygen/air mixture, or increased ambient oxygen delivered into an incubator) for ≥ 60 minutes at any time following birth.

Secondary outcomes:

For the infant:

- hypoglycaemia defined as any blood glucose concentration < 2.6 mmol/l;

- hypoglycaemia requiring treatment other than milk feeding (including dextrose gel, intravenous dextrose, glucagon);
- admission to a neonatal nursery and length of stay;
- severity of respiratory distress (severe: any intubation/mechanical ventilation and/or need for surfactant therapy; moderate: respiratory support (sum of mechanical and non-invasive) required for >24 hours; mild: the remainder requiring respiratory support for ≥60 minutes but <24 hours). The maximum appropriate mean airway pressure [MAP] for those requiring mechanical ventilation or nasal CPAP, and maximum appropriate fractional inspired oxygen [FiO₂] for those requiring any form of respiratory support will also be recorded. For those on HiFlo, the maximum appropriate flow rate will be recorded.
- need for, and duration of, all forms of respiratory support (including all forms of respiratory support described in the primary outcome);
- use of exogenous surfactant;
- pneumothorax or air leak requiring drainage;
- presence of x-ray features suggestive of hyaline membrane disease or transient tachypnoea of newborn (independently adjudicated by a neonatal radiologist blinded to treatment allocation) in a subset of babes who require chest x-ray as part of clinical care.

For the mother:

- requirement for additional insulin therapy after administration of study drug;
- requirement for hospital admission between randomisation and CS;
- highest blood glucose concentration recorded between randomisation and birth;
- maternal infection from the time of randomisation up until 6 weeks' postpartum including chorioamnionitis; maternal pyrexia ≥38°C; wound infection requiring antibiotic or surgical /radiological (e.g. ultrasound-guided drainage) treatment;
- maternal reported side effects of the study drug;
- maternal mental health assessed using the Edinburgh Postnatal Depression scale (EPDS);^{56,57}
- maternal general health prior to randomisation and at 6 weeks post partum assessed using the SF12⁵⁸ and AQoL8D.⁵⁹
- breast feeding rates at hospital discharge and 6 weeks' post-partum.

[figure not shown]
Assessment of blinding: We will assess the ability to blind participants, clinicians and research staff to the treatment allocation in a subset of participants. This information will be used in interim analyses (if required) and will be collected and reported to ensure transparency regarding the conduct of the trial.

Health economics: We will assess the economic costs and benefits of this intervention at 6 weeks post partum and again at 2 years post partum under the supervision of [name], who is a health economist. This will involve estimating the costs of administering the intervention compared with not administering the intervention. The hospital costs associated with each infant's birth admission will be obtained from administrative records and will reflect factors such as length of stay and admission to the neonatal nursery. Incremental cost effectiveness will be presented as a cost per case of respiratory morbidity avoided, a cost per case of respiratory support avoided and a cost per neonatal nursery admission avoided for the intervention group compared with the placebo group. Extensive one way and probabilistic sensitivity analyses will be conducted.

STUDY DESIGN

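### X-ray features of HMD or TTN are defined only in infants who need a chest x-ray, a post-randomisation subset that treatment is expected to shrink, and no all-infant denominator is stated

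*Protocol*

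**What the plan says.** Protocol Section 4 (Outcome Measures, secondary outcomes for the infant) lists "presence of x-ray features suggestive of hyaline membrane disease or transient tachypnoea of newborn". The films are to be "independently adjudicated by a neonatal radiologist blinded to treatment allocation", and the item closes with the restriction "in a subset of babes who require chest x-ray as part of clinical care". Other items in the same list, such as surfactant use and air leak needing drainage, carry no such restriction.

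Section 8.2 gives the general rule: "Outcomes will be compared between the intervention and control groups using an intention-to-treat analysis". Binary outcomes are analysed by logistic regression, with generalised estimating equations for infant outcomes. Neither section says how an infant without a film is counted.

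Section 3.3 hypothesises that treatment will "reduce the incidence and severity of neonatal respiratory morbidity". Section 8.1 powers the trial on respiratory distress falling from 6% to 3%.

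**The concern.** A clinical chest x-ray is ordered after randomisation, generally because the infant has breathing difficulty. On the trial's own hypothesis, treatment changes how many infants reach that point and how ill they are. The x-rayed infants in the two arms are then different kinds of infants, and comparing the proportion with HMD or TTN features between them is no longer a randomised comparison. Blinded adjudication protects the reading of each film but not the selection of who has one.

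At stake is a secondary outcome that could show no difference where treatment works. Section 3.2 distinguishes surfactant deficiency from TTN as causes of respiratory morbidity, so readers will look at this outcome for that distinction.

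**Working it through.** **Inputs from the protocol.** 6% versus 3% respiratory distress, 90% power, two-sided alpha 0.05, continuity correction, 3% drop-out, 1100 mothers per arm (Section 8.1).

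**Assumptions, because the protocol gives no x-ray rate and no HMD/TTN split.** X-rayed infants are those with respiratory morbidity. HMD is seen in one third of control films. Either HMD or TTN is seen in 80% of control films. One infant is counted per mother.

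**Step 1: the plan's own figure.** The uncorrected two-proportion formula gives 1002 per arm, and 1068 with continuity correction. Dividing by the retained share, 1068/0.97 = 1101.03, rounded up to 1102 per arm or 2204 in total, against 2200 stated. The figure is reproduced. Evaluable per arm: 1100 × 0.97 = 1067.

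**Step 2: expected films.** Control 1067 × 0.06 = 64; betamethasone 1067 × 0.03 = 32.

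**Step 3: the relation.** The proportion with the finding among x-rayed infants is (risk of the finding in all infants) / (risk of x-ray). Therefore

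x-rayed-only RR = (true RR of the finding in all infants) / (RR of being x-rayed).

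Here the RR of being x-rayed is 0.03/0.06 = 0.50, so the x-rayed-only RR is twice the true RR.

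**Step 4: HMD alone.** Control: 2.0% of all infants have HMD on film and 4.0% are x-rayed without it. The x-ray rate under betamethasone is held at 3.0%.

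| True RR, all infants | Betamethasone: HMD / other x-rayed | RR, other reasons | Share with HMD among x-rayed, control vs betamethasone | x-rayed-only RR |
|---|---|---|---|---|
| 0.25 | 0.5% / 2.5% | 0.625 | 33% vs 17% | 0.50 |
| 0.50 | 1.0% / 2.0% | 0.50 | 33% vs 33% | 1.00 |
| 0.75 | 1.5% / 1.5% | 0.375 | 33% vs 50% | 1.50 (odds ratio 2.00) |
| 0.90 | 1.8% / 1.2% | 0.30 | 33% vs 60% | 1.80 (odds ratio 3.00) |

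Equal effects on all reasons for x-ray make the difference vanish. The direction reverses only when the other reasons fall proportionally more than HMD.

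**Step 5: HMD or TTN combined.** Control: 4.8% with the finding and 1.2% x-rayed without it. True RRs of 0.45, 0.50 and 0.55 become 72%/80% = 0.90, 80%/80% = 1.00 and 88%/80% = 1.10. A true RR of 0.60 gives 96%/80% = 1.20, but needs films without either feature to fall by 90% (1.2% to 0.12%). The ceiling is 100%/80% = 1.25.

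**Step 6: dependence on the x-ray rate.** If treatment did not change the x-ray rate at all (RR 1), a true halving would show undistorted as 0.50. Between that and the assumed RR of 0.50, a true halving shows as something between 0.50 and 1.00.

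**The case against.** The strongest reply is that Section 4 only says where films will come from: clinical care, with no research x-rays. On that reading it fixes ascertainment, the general rule in Section 8.2 supplies an all-infant denominator, and the details belong in a statistical analysis plan. This reading is possible, and it is why an outright contradiction of intention to treat, which a reader might infer, is not established. But the protocol nowhere states it. The restriction sits inside the outcome definition, and the intention-to-treat sentence does not say how infants without a film count. The population is therefore fixed in words that, followed literally, give the wrong comparison.

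A reader might also infer that the analysis would signal harm where there is benefit. The documents do not support that as a prediction. Reversal needs unequal effects, and the x-ray rate and HMD share are assumed. The earlier review cited in Section 3.2 gives RR 0.48 for respiratory distress and 0.43 for TTN. Taking 0.48 as a proxy for HMD, and supposing all films show one or the other, the odds ratio among x-rayed infants would be 0.48/0.43 = 1.12, close to null. (The protocol itself calls that evidence low quality and notes a retraction.) With 64 versus 32 films, even a contrast of 33% versus 50% would be detected with only about 36% power, and it would be read beside an all-infant primary outcome.

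Nor does any section make this outcome the trial's evidence on mechanism. Surfactant use and severity of respiratory distress also bear on surfactant deficiency and are not limited to x-rayed infants.

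**Conclusion.** The point holds in a limited form. As worded, one secondary outcome is conditioned on a post-randomisation event that the trial expects to halve, and a comparison within that subset would not be protected by randomisation. The main consequence is lost signal: if all reasons for x-ray fall equally, a true halving of HMD appears as RR 1.00. Reversal is a possibility for HMD alone (true RR 0.75 appearing as 1.50). For the combined outcome, true RRs of 0.45 to 0.55 are pulled to about 0.90 to 1.10. All these figures rest on the assumption that x-rayed infants are those with respiratory morbidity and on the assumed shares of film findings; that treatment shrinks the subset is the trial's hypothesis, not an observation. The primary outcome and the sample size are unaffected. The change is worth making because it is nearly free.

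**What to change.** In Section 4, replace the item with two binary outcomes over all liveborn infants of randomised women: a clinically indicated chest x-ray with adjudicated HMD features, and the same for TTN. Count infants without a clinically indicated film as no event. Report the x-ray rate by arm, and give the proportions among x-rayed infants descriptively, without a treatment-effect test.

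The cost is a change of wording; the films and the blinded reader are already planned. If the present text means that only some clinical films would be read, the rest should be added: about 64 + 32 = 96 films in total under the assumption above.

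One limitation remains. The all-infant outcome still depends on who orders films, and ordering could differ by arm if clinicians guess the allocation or know it after the open-label change allowed in Sections 7.4 and 8.3. Reporting the x-ray rate by arm lets readers judge this.
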